1.2 Research hypothesis

Administration of 20 μ g AZD8848 three times weekly, as compared to 60 μ g once weekly, will result in prolonged reduction of nasal symptoms after allergen challenge and/or increased tolerability to the substance.

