2. STUDY OBJECTIVES

2.1 Primary objective

Table 1 Primary Objective

To compare the efficacy of $60~\mu g$ AZD8848 once weekly with $20~\mu g$ AZD8848 three (3) times weekly and with placebo when administered intranasally to seasonal allergic rhinitis patients out of season in a nasal allergen challenge model.

Variables	Description
Reflective Total Nasal Symptom Score (TNSS) (recall period 12 h, twice daily during Visit 15)	Nasal symptoms
Reflective TNSS (recall period 10 min) after allergen challenge	Nasal symptoms
Peak Nasal Inspiratory Flow (PNIF) (twice daily during Visit 15)	
PNIF 10 min after allergen challenge	

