12.2 Methods of statistical analyses

All AEs will be listed for each patient and summarized by system organ class and preferred term by using MedDRA vocabulary. AEs will be analysed in terms of descriptive statistics and qualitative analysis.

Safety data will individually be listed and graphically illustrated, presented as descriptive statistics (for example median, mean, range and standard deviation) and mean value plots for each treatment and assessment time. In addition changes in safety variables over time will be presented by shift and scatter plots if existing. Values below and above AstraZeneca extended reference limits will be highlighted.

Efficacy data from this study will be pooled with the same type of data from the Tol/PoP study (D0540C00003), which was virtually identical to the present study in terms of selection criteria and study conduct. The one main difference is that in the present study, women are allowed to participate. The Tol/Pop study featured treatment arms with placebo (n 34) and 60 μg AZD8848 once weekly (n 34) respectively; efficacy data from these arms will be pooled with data from the corresponding arms in the present study.

For all comparisons between treatments the efficacy data (reflective TNSS, individual symptom scores, PNIF) and pharmacodynamic variables (biomarkers in nasal lavage and plasma) will be analysed using analysis of variance (ANOVA) models with treatment and centre as factors and, for biomarkers and clinic PNIF measurements, the baseline value as covariate. When appropriate, multiplicative models will be used.

THIS

Clinical Study Protocol Drug Substance AZD8848 Study Code D0540C00014 Edition Number 1

The covariate in the respective model, the baseline value, will be the last value before first dose of the study drug. From the respective model the pairwise treatment differences between AZD8848 (once weekly and three times weekly, respectively) and placebo will be estimated and confidence intervals and p-values will be calculated. For biomarkers not reported in the CSR, appropriate statistical methods will be used.

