12.3 Determination of sample size

The sample size for this study was selected to be consistent with the research hypothesis as described in Section 1.2.

From previous studies with Rhinocort® in allergic rhinitis using the same provocation model, it has been estimated that the standard deviation for TNSS (both morning and evening) is about 1.5 units. In the preceding Tol/PoP study (D0540C00003), the residual sample standard deviation in the analysis of variance (ANOVA) models was slightly higher however; about 2 units. Since the data from this study will be pooled with the data from the present one we assume a standard deviation of 2 units here too.

A planned total of 70 completed patients in proportions 1:3:1 for the treatments arms $60 \mu g$ AZD8848 once weekly, $20 \mu g$ AZD8848 three times weekly and placebo, respectively, yields 14, 42 and 14 patients respectively in these arms.

Using a one-sided test at 5 % significant level with a sample size of 42 patients in the 20 μ g AZD8848 three times weekly arm and 34+14 = 48 patients in the 60 μ g AZD8848 once weekly arm (obtained after pooling with the Tol/PoP study), with another 34+14 = 48 placebo patients contributing to the estimate of the standard deviation, will then give a 76 % chance to detect a difference of 1 unit between the two AZD8848 arms.

The number of patients that will agree to participate in the genetic research is unknown. It is therefore not possible to establish whether sufficient data will be collected to allow a formal statistical evaluation or whether only descriptive statistics will be generated.

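### The contrasts listed in Section 12.2 omit 20 µg three times weekly versus 60 µg once weekly, the comparison that the hypothesis, the primary objective and the power statement rest on

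*Protocol*

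**What the plan says.** Four places in the protocol bear on which treatments are compared.

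- **Section 1.2** sets 20 µg three times weekly against 60 µg once weekly and expects that the former "will result in prolonged reduction of nasal symptoms after allergen challenge and/or increased tolerability to the substance". Placebo is not mentioned.
- **Section 2.1** compares 60 µg once weekly with two things: "AZD8848 three (3) times weekly and with placebo when administered intranasally to seasonal allergic rhinitis patients out of season". The regimen comparison comes first, and 60 µg versus placebo is also part of the primary objective.
- **Section 12.3** states: "The sample size for this study was selected to be consistent with the research hypothesis as described in Section 1.2". It then assumes a one-sided 5% test and concludes that the numbers "will then give a 76 % chance to detect a difference of 1 unit between the two AZD8848 arms". Placebo patients enter that calculation only through the estimate of the standard deviation.
- **Section 12.2** opens with a general model sentence, "For all comparisons between treatments the efficacy data (reflective TNSS, individual symptom scores, PNIF) and pharmacodynamic variables", to be analysed by ANOVA with treatment and centre as factors. It then names what is taken from the model: "the pairwise treatment differences between AZD8848 (once weekly and three times weekly, respectively) and placebo will be estimated", with confidence intervals and p-values.

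**The concern.** Section 12.2 is where the protocol says which differences will be reported, and its list is specific. The word respectively ties each regimen to placebo, so the sentence cannot be read as covering all three pairs. The one pair left out is the one that Sections 1.2 and 12.3 are about and that 2.1 names first.

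A statistician who programs the contrasts from 12.2 would report 60 µg versus placebo and 20 µg versus placebo. The regimens could then be compared only indirectly, for instance by noting that one reached significance against placebo and the other did not. That is not a test of their difference. If the missing contrast were added only after the data had been seen, it would look post hoc even though the trial was sized for it.

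This is not detail that can be left to a statistical analysis plan. The protocol itself lists the contrasts, so such a plan would have to follow an incomplete list or depart from it.

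**Working it through.** **1. Inputs, all from Section 12.3.** SD 2 units; difference 1 unit; one-sided 5%. Patients: 42 on 20 µg three times weekly, 34 + 14 = 48 on 60 µg once weekly, 34 + 14 = 48 on placebo (the 34s come from the earlier Tol/PoP study).

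**2. Reproducing the 76%.**
- Standard error of 20 µg minus 60 µg: 2 × √(1/42 + 1/48) = 0.423.
- Difference in standard-error units: 1 / 0.423 = 2.37.
- Normal approximation: Φ(2.37 − 1.645) = 76.5%.
- Non-central t, three-arm error df 42 + 48 + 48 − 3 = 135: 76.1%.
- Same calculation with a two-sided 5% test: 65.2%.

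The stated 76% is therefore a one-sided test between the two active arms, with residual error from a three-arm model.

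**3. Contrast by contrast.**

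| Contrast | 1.2 | 2.1 | Power stated in 12.3 | Listed in 12.2 |
|---|---|---|---|---|
| 20 µg three times weekly vs 60 µg once weekly | yes | yes, first | 76% | **no** |
| 60 µg once weekly vs placebo | no | yes | none | yes |
| 20 µg three times weekly vs placebo | no | not named | none | yes |

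The contrast in the first row is supported by three sections and missing from the fourth.

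**4. Can the two listed results stand in for the missing one?** In one additive model, subtracting the two placebo differences gives the regimen difference as a point estimate. The precision does not follow in the same simple way, because both differences share the placebo mean.
- Variance of 20 µg minus placebo: 4 × (1/42 + 1/48) = 0.1786.
- Variance of 60 µg minus placebo: 4 × (1/48 + 1/48) = 0.1667.
- Their covariance, from the shared placebo mean: 4/48 = 0.0833.
- Correct variance of the difference: 0.1786 + 0.1667 − 2 × 0.0833 = 0.1786, so SE = 0.423.
- Treating the two as independent: √(0.1786 + 0.1667) = 0.588, about 39% too wide (0.588 / 0.423 = 1.39).

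The interval and p-value have to be taken from the model as a contrast in their own right.

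**5. After the change.** Adding the contrast uses the same model, patients and SD. SE stays 0.423 and power stays 76.1%.

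**The case against.** The strongest reply is that the protocol read as a whole does provide for the comparison. Section 12.3 presupposes a one-sided 5% test between the active arms. The opening of 12.2 gives a model for all treatment comparisons, 2.1 names this one first, and the placebo sentence does not say only. A team that read everything would have contrast, model, level and sidedness. This stands as a limit on the claim. A reader might infer from 12.2 that the regimen difference is never estimated or tested anywhere; the documents do not support that. It does not remove the conflict, because the general sentence fixes the model, while the later one fixes which differences are reported and omits this one.

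Three further inferences also go too far.

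- **That the placebo contrasts should become merely supportive.** Section 2.1 makes 60 µg versus placebo part of the primary objective, so demoting it would create a new mismatch.
- **That 12-hour TNSS averaged over the challenge period is the variable behind the sample size.** Section 12.3 refers only to morning and evening TNSS and gives no averaging window, while 11.1 defines two. Ranking the variables in Table 1 can be left to the statistical analysis plan. Nor is the lack of a power figure for 20 µg versus placebo an error, since 12.3 deliberately powers the Section 1.2 hypothesis.
- **That misleading results would arise in about a third of trials.** If both regimens had the same true effect over placebo, exactly one would reach one-sided significance in about 34% of trials at an effect of 0.7 units. That effect is an assumption found nowhere in the protocol and lies near the worst case: the figure is 25% at 1.0 unit and 4% at 1.5. The protocol also does not propose drawing conclusions in this way.

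**Conclusion.** The point holds as an internal contradiction. The Section 12.2 list conflicts with 1.2, 2.1 and 12.3 because it omits the contrast on which they agree. Applied literally, it would report no estimate, interval or p-value for the trial's own efficacy hypothesis. A point estimate could be recovered by subtraction, but its interval and p-value could not be read off the two listed results.

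The size is one missing contrast, and it is the only powered one: 76% stated, 76.1% recomputed. The recomputation takes 12.3's own assumptions as given: SD 2, 42 and 48 completed patients, pooling with the Tol/PoP study, one-sided 5%. It concerns the efficacy part of the hypothesis. The tolerability part is outside this contrast.

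**What to change.** In Section 12.2, add the 20 µg three times weekly minus 60 µg once weekly difference to the listed contrasts, with estimate, confidence interval and p-value from the same ANOVA. Name it as the test of the efficacy part of the Section 1.2 hypothesis at the one-sided 5% level of 12.3, which corresponds to a 90% two-sided interval. State the direction: for TNSS, 1.2 implies that a negative difference favours 20 µg three times weekly.

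Keep both placebo contrasts as they are, with 60 µg once weekly versus placebo remaining part of the primary objective.

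The cost is one or two sentences in 12.2. The sample size, allocation, visits and data collection are unaffected.

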12.3 Determination of sample size

The sample size for this study was selected to be consistent with the research hypothesis as described in Section 1.2.

From previous studies with Rhinocort® in allergic rhinitis using the same provocation model, it has been estimated that the standard deviation for TNSS (both morning and evening) is about 1.5 units. In the preceding Tol/PoP study (D0540C00003), the residual sample standard deviation in the analysis of variance (ANOVA) models was slightly higher however; about 2 units. Since the data from this study will be pooled with the data from the present one we assume a standard deviation of 2 units here too.

A planned total of 70 completed patients in proportions 1:3:1 for the treatments arms $60 \mu g$ AZD8848 once weekly, $20 \mu g$ AZD8848 three times weekly and placebo, respectively, yields 14, 42 and 14 patients respectively in these arms.

Using a one-sided test at 5 % significant level with a sample size of 42 patients in the 20 μ g AZD8848 three times weekly arm and 34+14 = 48 patients in the 60 μ g AZD8848 once weekly arm (obtained after pooling with the Tol/PoP study), with another 34+14 = 48 placebo patients contributing to the estimate of the standard deviation, will then give a 76 % chance to detect a difference of 1 unit between the two AZD8848 arms.

The number of patients that will agree to participate in the genetic research is unknown. It is therefore not possible to establish whether sufficient data will be collected to allow a formal statistical evaluation or whether only descriptive statistics will be generated.

13.2 Overdose

Serious intolerability resulting from drug administration cannot be excluded. There is no known antidote to AZD8848. No experience from patients who have overdosed AZD8848 is currently available. In case of known or suspected intolerability or overdose, symptomatic treatment as well as monitoring of vital functions should be performed, based on the judgment of the Investigator.

For the purpose of this study, an accidental or deliberate intake of higher doses of AZD8848 than planned according to the protocol is defined as an overdose and must be reported as such as described below;

- An overdose with associated AEs is recorded as the AE diagnosis/symptoms on the relevant AE modules in the eCRF and on the Overdose eCRF module
- An overdose without associated symptoms is only reported on the Overdose eCRF module

If an overdose with an AstraZeneca study drug occurs in the course of the study, then Investigators or other centre personnel inform appropriate AstraZeneca representatives within one (1) day, ie, immediately but no later than the end of the next business day of when he or she becomes aware of it.

Clinical Study Protocol Drug Substance AZD8848 Study Code D0540C00014 Edition Number 1

The designated AstraZeneca representative works with the Investigator to ensure that all relevant information is provided to the AstraZeneca patient safety data entry site.

For overdoses associated with SAE, standard reporting timelines apply, see Section 6.4. For other overdoses, reporting should be done within 30 days.

13.3 Pregnancy

All pregnancies and their subsequent outcome (spontaneous miscarriage, elective termination, ectopic pregnancy, normal birth or congenital abnormality) should be reported to AstraZeneca using the appropriate forms.

13.3.1 Maternal exposure

WOCBP must use reliable contraception, see Section 5.1.2. In addition, pregnancy tests will be performed on WOCBP at Visits 1, 2, 8, 15, 16, and 17. For women not of childbearing potential pregnancy tests will be performed on Visits 1, 2 and 16. The tests prior to dose must be available before drug administration.

In the event of suspected pregnancy, the test should be repeated and if a pregnancy occurs, the patient must be discontinued from treatment and the pregnancy must be documented and reported as described below.

Pregnancy itself is not regarded as an adverse event unless there is a suspicion that the investigational product under study may have interfered with the effectiveness of a contraceptive medication. Congenital abnormalities/birth defects and spontaneous miscarriages should be reported and handled as SAEs. Elective abortions without complications should not be handled as AEs. The outcome of all pregnancies (spontaneous miscarriage, elective termination, normal birth or congenital abnormality) must be followed up and documented even if the patient was discontinued from the study.

If any pregnancy occurs in the course of the study, the Investigator(s) or other centre personnel must inform appropriate AstraZeneca representatives immediately but not later than the end of the next business day of when he/she becomes aware of it. The designated AstraZeneca representative works with the Investigator to ensure that all relevant information is provided to the appropriate AstraZeneca Patient safety data entry site within 30 calendar days.

The PREGREP module in the eCRF is used to report the pregnancy and the PREGOUT is used to report the outcome of the pregnancy.

13.3.2 Paternal exposure

Male patients should avoid unprotected intercourse with a pregnant woman from first dose until Visit 16 and avoid sperm donation and unprotected intercourse with WOCBP not using birth control from first dose until Visit 16 + 3 weeks, since the potential for chromosomal

Clinical Study Protocol Drug Substance AZD8848 Study Code D0540C00014 Edition Number 1

aberrations in male gametes, and possible teratogenic effects thereof, have not yet been thoroughly investigated.

Pregnancy of patients partners is not considered to be an adverse event. If the Investigator receives information that a pregnancy has occurred during the study despite these restrictions, the Investigator should ask the patient whether this information can be forwarded to AstraZeneca. If the permission is granted, the Investigator should inform the AstraZeneca representative. The Investigator will follow up and document the outcome of the pregnancy (spontaneous miscarriage, elective termination, normal birth or congenital abnormality), as described in Section 13.3.1.

